---

## Study Status

Record Verification: January 2023

Overall Status: Completed

Study Start: April 13, 2022 [Actual]

Primary Completion: October 15, 2022 [Actual]

Study Completion: December 30, 2022 [Actual]

## Oversight

U.S. FDA-regulated Drug: No

U.S. FDA-regulated Device: No

U.S. FDA IND/IDE: No

Human Subjects Review: Board Status: Approved

Approval Number: FMHS 448-0122

Board Name: Faculty of Medicine & Health Sciences Research Ethics Committee

Board Affiliation: Medical School

[contact]

Email: [contact]

Address:

[name]

Queen's Medical Centre Campus  
Nottingham University Hospitals  
[name]  
United Kingdom

Data Monitoring: No

FDA Regulated Intervention: No

## Study Description

**Brief Summary:** A variety of biomechanical gait modification interventions can elevate knee loading and improve knee symptoms in knee osteoarthritis patients. However, there was a lack of acceptability and adherence regarding modification interventions without any explanation.

Thus, this study investigates the feasibility and acceptability of foot insoles as a gait modification tool among Saudi Arabian knee osteoarthritis patients and physiotherapists.

This study aims to answer the following:

- Which gait modification intervention is most likely to be implemented in Saudi Arabia (SA) clinical practice, taking context, patients' clinical and research evidence into consideration?
- In Saudi Arabia, can this proposed foot-insole intervention be implemented? Is there sufficient experience among physiotherapists regarding gait modification to deliver it, and will patients engage with it? How can KOA rehabilitation outcomes be evaluated in the future?

The participants will be conducted over three phases:

1. The patients' interview and therapists' focus group discussion will be used to examine KOA patients' and clinicians' perspectives on enabling and accepting gait modifications in phase 1.
2. The feasibility study will explore how a small number of KOA patients tolerate gait modifications and consider the most relevant outcome measures, such as pain and function, in phase (2).
3. A small group of knee osteoarthritis patients and their physiotherapists who participated in phase (2) will be asked to participate in a descriptive survey in phase (3). To examine the acceptability and feasibility of the study intervention in phase (2).

**Detailed Description:** Since several different types of gait modifications have been studied, it has been challenging to determine which are most likely to be used by patients and healthcare professionals.

A notable number of Saudi Arabians suffer from knee osteoarthritis (KOA), which reported a 29.5% prevalence of KOA; another recent study reported a 24.5% prevalence of KOA among the elderly. A 2002 study found that 30.8% of those aged 46-55 and 60.6% aged 66-75 were affected. Thus, KOA is roughly equally distributed between genders and is more prevalent among elderly and overweight individuals, so policymakers should focus on raising awareness to prevent and treat affected individuals. The healthcare system in SA is publicly funded and accessible; 79% of patients use the public system, and the rest obtain private care. In most cases, private patients have insurance coverage. The public healthcare system has three primary, secondary, and tertiary care levels. Rehabilitation and gait modification investigations are not available at the

primary level.

This snapshot of the literary review raises questions about the viability of the long-term use of learned/assistive gait modifications. The studies reported dissatisfaction with the gait modification approach but gave no reasons. Since most studies focus on results in a short time or a specific area, pre-training courses measuring acceptability and commitment can fill the gaps in previous studies. After determining the importance of gait modification, the question becomes, should it be integrated into the therapy strategy or other rehabilitative methods to increase the treatment's clinical efficacy? It is essential to understand the practices, views and expectations of KOA patients and health professionals concerning gait modifications.

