## Study Design

Study Type: Interventional

Primary Purpose: Other

Study Phase: N/A

Interventional Study Model: Single Group Assignment

A gait modification (Lateral wedge insole) program will be conducted over 4 to 6 weeks in the physiotherapy gym or adjusted treadmill and outside the clinic during the day (at least 8 hours per day).

- During the session, the researcher will observe participants inside the clinic and ensure that the modified gait application is applied, and outside the clinic will be followed by telephone.
- Participants will walk on the gym floor or an adjusted treadmill for at least 15 to 20 minutes during each session. Participants will be instructed to use the mirror for feedback and achieve the target modified gait procedure. However, it will be emphasised gait modification procedures exhibited at baseline pain and function, and then at the end of the trial, it will focus on subjects' acceptability.

Number of Arms: 1

Masking: None (Open Label)

Allocation: N/A

Enrollment: 17 [Actual]

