## Arms and Interventions

Arms	Assigned Interventions

Experimental: Feasibility intervention
 
The intervention will be foot insole (lateral wedge) insole, which has already been delivered in routine UK NHS and SA environments by at least one physiotherapist. Clinical testing will be done with 15-25 knee osteoarthritis subjects. These individuals will be assigned to a single intervention group for 4-6 weeks of re-gait training intervention. It involves a personalised gait retraining programme (sizable insole) for the KOA subjects to evaluate the impact on knee pain and improve function. It is set within 4-6 weeks of VAS and the WOMAC tools for knee pain & function outcome.
	
Device: Lateral Wedge insole
 
Insoles with lateral wedges are placed in patients' shoes to control biomechanical knee loading on the medial side of the knee. Insoles with lateral wedges are designed to be thinner on the inside (medially of the foot) and thicker on the outside (laterally of the foot) to relieve knee biomechanical loading parameters.
 
Other Names:
 
 
• Footwear insole
 
• Ankle foot orthoses
 

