## Outcome Measures

### Primary Outcome Measure:

#### 1. Pain level

The change from baseline pain intensity level at 6-weeks, based on the nine points of a visual analogue scale, where 0 represents (no pain) and 9 represents (worst pain).

[Time Frame: 6 weeks post-intervention.]

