#### 3. Likert scale

Measuring knee osteoarthritic subjects' satisfaction based on the 5 point Likert scale survey.

[Time Frame: 6 weeks post-intervention.]

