#### 4. Likert scale

Measuring therapists' agreement based on the 5-point Likert scale survey.

[Time Frame: 6 weeks post-intervention supervision.]

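### Two primary outcomes depend on the phase 3 survey, but the protocol does not fix who is asked, and its wording permits a selected part of the phase 2 group

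*Protocol*

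**What the plan says.** The protocol's Study Description sets out three phases. Phase 2 is the insole intervention: "The feasibility study will explore how a small number of KOA patients tolerate gait modifications". Phase 3 is a survey: "A small group of knee osteoarthritis patients and their physiotherapists who participated in phase (2) will be asked to participate in a descriptive survey". Its stated purpose is "To examine the acceptability and feasibility of the study intervention in phase (2".

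Under Outcome Measures, the heading "Primary Outcome Measure" opens a numbered list of four items, and no secondary heading follows in the text shown. Item 3 is "Measuring knee osteoarthritic subjects' satisfaction based on the 5 point Likert scale survey" and item 4 is "Measuring therapists' agreement based on the 5-point Likert scale survey". Neither item limits the survey to some of the participants. Study Design likewise says, without restriction, that attention at the end of the trial turns to whether subjects found the intervention acceptable.

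On numbers, Arms and Interventions states "Clinical testing will be done with 15-25 knee osteoarthritis subjects", and Study Design records an actual enrolment of 17.

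**The concern.** The survey is the evident source of the two Likert outcomes, so whoever is asked to complete it defines the population for two of the four primary outcomes. The protocol describes that population in one sentence, which gives no number, no rule for choosing people and no word on patients who gave up the insole or the sessions.

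A site could follow that sentence to the letter, survey a handful of patients and leave out those who stopped. The Study Description justifies the trial by poor acceptability and adherence in earlier work that went unexplained. Patients who stopped early are therefore the people whose ratings bear most directly on the question. If they are missing, the satisfaction figure describes those who were asked, not those who were given the insole.

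**Working it through.** The protocol states no figure for the survey (no number to be asked, no expected response, no precision target), so there is nothing to reproduce. The check has two parts.

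**1. Which readings does the text allow?**

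- *Whole group.* Phase 2 is already described as a small number of patients, planned at 15 to 25. A small group who took part in phase 2 can simply be that cohort. The unrestricted wording of outcome item 3 and of Study Design fits this reading.
- *Part of the group.* The phase 3 sentence does not refer back to the phase 2 patients as a body. It introduces a small group, with an indefinite article, of people who took part in phase 2. Nothing in the sentence excludes a subset.

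Both readings are open, and no other section shown settles the matter.

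**2. What is at stake if only part of the group is asked?**

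Inputs:

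- N = 17, the enrolment in Study Design. I take all 17 to be phase 2 patients, which is an assumption; the figure lies within the planned 15 to 25.
- m = number asked, with all of them answering (assumed).
- s = number satisfied among them (assumed).

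The proportion satisfied among all N lies between two extremes:

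- none of those not asked is satisfied: s / N
- all of those not asked are satisfied: (s + N − m) / N

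Main illustration, m = 10 and s = 9:

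- reported: 9/10 = 90%
- lowest: 9/17 = 52.9%
- highest: (9 + 7)/17 = 16/17 = 94.1%

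Other assumed sizes:

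| Asked (m) | Satisfied (s) | Reported | Lowest of 17 | Highest of 17 |
|---|---|---|---|---|
| 6 | 5 | 83% | 5/17 = 29% | 16/17 = 94% |
| 10 | 8 | 80% | 8/17 = 47% | 15/17 = 88% |
| 15 | 12 | 80% | 12/17 = 71% | 14/17 = 82% |
| 17 | 14 | 82% | 14/17 = 82% | 14/17 = 82% |

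If everyone asked is satisfied, the reported figure is 100%, but the share of all 17 could be as low as 6/17 = 35% with 6 asked, 10/17 = 59% with 10 and 15/17 = 88% with 15.

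The width of the range is (N − m)/N, so each patient not asked adds 1/17 = 5.9 percentage points. Asking all 17 and getting all answers brings it to zero. These ranges concern only who is left out; sampling error is separate.

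The range lies on both sides of the reported figure. In the main illustration there is more room below (90 − 52.9 = 37.1 points) than above (94.1 − 90 = 4.1 points), but that follows from an assumed figure near 100% and does not show which way any bias runs.

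No such range can be given for item 4, because the text shown does not state how many physiotherapists took part.

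**The case against.** The strongest reply is that the protocol never says the survey is limited to a subset. It does not speak of some of the patients or of selected patients. Phase 2 is small in the protocol's own words, and the outcome list and Study Design refer to subjects without restriction. This stands. A reader might infer that phase 3 by design surveys only part of the phase 2 group; the text does not establish that.

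A reader might also infer that the researcher who observes the sessions would pick whom to ask, and that satisfaction would therefore be overstated. The protocol does not say who issues the invitations, nor who makes the telephone follow-up. The loss of dissatisfied patients is a plausible mechanism, not a documented one, and the ranges above fix no direction.

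It is also fair to say that views on accepting gait modification are explored in the phase 1 interviews and focus groups. Phase 3 is a descriptive survey with 5-point ratings, so the point concerns the satisfaction and agreement ratings, not the loss of patients' reasons.

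Finally, the choice of denominator and the display of non-responders are commonly left to a statistical analysis plan, which is not shown. That is accepted, and their absence is not held against the protocol. Who is asked is different: it is a rule of data collection, and no analysis plan can recover answers from people who were never approached.

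**Conclusion.** The point holds as a gap in the invitation rule for two primary outcomes. The wording permits a survey of a selected part of the phase 2 group, and nothing else in the protocol closes that option. If only part was asked, the result could be biased in either direction, and upward if patients who stopped early were left out.

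The size is illustrative: with 10 of 17 asked and 9 satisfied, 90% is compatible with 53% to 94% of those enrolled. This rests on assumed values of m and s, on complete response among those asked, and on all 17 being phase 2 patients. If all 17 were asked and answered, the concern disappears.

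The documents do not support the conclusion that a subset was in fact surveyed or that satisfaction was in fact overstated.

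**What to change.** Replace the phase 3 sentence with: *All patients enrolled in phase 2, including those who stopped the insole or sessions early, and all participating physiotherapists, will be asked to complete the survey.* Report how many were asked and how many answered, out of all enrolled. Patients no longer attending could be approached by telephone, which Study Design already uses for follow-up outside the clinic. This wording serves under either reading: if everyone was always meant, it only makes that explicit.

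The protocol records the study as completed, so the remedy for this trial lies in its report. State how many of the 17 were asked, how they were chosen and how many answered, with the same for physiotherapists, and limit the acceptability conclusion to what those numbers support. The revised sentence is then for any follow-on trial.

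The cost is one sentence and a few extra questionnaires or calls. The satisfaction figure may become less favourable.

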## Conditions

Conditions: Osteoarthritis, Knee  
Pain  
Biomechanical Lesion

Keywords: Knee osteoarthritis  
Insole  
Biomechanical  
Saudi Arabia

## Study Design

Study Type: Interventional

Primary Purpose: Other

Study Phase: N/A

Interventional Study Model: Single Group Assignment

A gait modification (Lateral wedge insole) program will be conducted over 4 to 6 weeks in the physiotherapy gym or adjusted treadmill and outside the clinic during the day (at least 8 hours per day).

- During the session, the researcher will observe participants inside the clinic and ensure that the modified gait application is applied, and outside the clinic will be followed by telephone.
- Participants will walk on the gym floor or an adjusted treadmill for at least 15 to 20 minutes during each session. Participants will be instructed to use the mirror for feedback and achieve the target modified gait procedure. However, it will be emphasised gait modification procedures exhibited at baseline pain and function, and then at the end of the trial, it will focus on subjects' acceptability.

Number of Arms: 1

Masking: None (Open Label)

Allocation: N/A

Enrollment: 17 [Actual]

## Arms and Interventions

Arms	Assigned Interventions

Experimental: Feasibility intervention
 
The intervention will be foot insole (lateral wedge) insole, which has already been delivered in routine UK NHS and SA environments by at least one physiotherapist. Clinical testing will be done with 15-25 knee osteoarthritis subjects. These individuals will be assigned to a single intervention group for 4-6 weeks of re-gait training intervention. It involves a personalised gait retraining programme (sizable insole) for the KOA subjects to evaluate the impact on knee pain and improve function. It is set within 4-6 weeks of VAS and the WOMAC tools for knee pain & function outcome.
	
Device: Lateral Wedge insole
 
Insoles with lateral wedges are placed in patients' shoes to control biomechanical knee loading on the medial side of the knee. Insoles with lateral wedges are designed to be thinner on the inside (medially of the foot) and thicker on the outside (laterally of the foot) to relieve knee biomechanical loading parameters.
 
Other Names:
 
 
• Footwear insole
 
• Ankle foot orthoses
 

## Outcome Measures

### Primary Outcome Measure:

#### 1. Pain level

The change from baseline pain intensity level at 6-weeks, based on the nine points of a visual analogue scale, where 0 represents (no pain) and 9 represents (worst pain).

[Time Frame: 6 weeks post-intervention.]

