#### 2. Western Ontario and McMaster Universities Arthritis Index-total

The change from baseline pain, stiffness and physical activity levels at 6-weeks.

Each question is scored from 0 to 4, which are: None (0), Mild (1), Moderate (2), Severe (3), and Extreme (4).

Scores are summed for each subscale, ranging from 0-20 for pain, 0-8 for stiffness, and 0-68 for Physical Function.

A higher WOMAC score indicates worse pain, stiffness, and functional limitations.

[Time Frame: 6 weeks post-intervention.]

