## Eligibility

Minimum Age: 45 Years

Maximum Age:

Sex: All

Gender Based:

Accepts Healthy Volunteers: No

Criteria: Inclusion Criteria:

KOA Patient participants:

- Adults aged above 45 years old.
- Both Male & Female.

- Radiographically or KOA participants meet any diagnostic classification guidelines/criteria (American College of Rheumatology classification criteria) or any eligible diagnostic guidelines.
- Typical knee pain while walking > 3 on an 11-point scale (0-10) in at least one knee pain or tenderness, primarily in the medial knee.

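### Does describing a 0-to-9 pain scale as having nine points undermine the first primary outcome?

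*Protocol*

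**What the plan says.** Under Outcome Measures, item 1 (Pain level), the primary pain outcome is the change from baseline to six weeks in pain intensity, "based on the nine points of a visual analogue scale, where 0 represents (no pain) and 9 represents (worst pain"). The sentence therefore gives a count (nine) and two labelled ends (0 and 9).

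Three other places bear on it:

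- Eligibility uses a separate item: "Typical knee pain while walking > 3 on an 11-point scale (0-10").
- Arms and Interventions names the instrument without a range: "It is set within 4-6 weeks of VAS and the WOMAC tools for knee pain".
- Outcome Measures, item 2 (WOMAC), lists five labelled responses: "Each question is scored from 0 to 4, which are: None (0), Mild (1), Moderate (2), Severe (3), and Extreme (4").

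Study Design refers to "gait modification procedures exhibited at baseline pain and function" without naming a scale. Study Status gives "Overall Status: Completed", and Study Design records one group, open label, with 17 enrolled.

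**The concern.** A primary outcome should have an unambiguous range, because the range gives a change score its meaning. Here the count and the two anchors cannot all be right if points means response options. Either the count is wrong or one anchor is. The only other mention of the VAS gives no range.

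The screening item adds to the unease. It asks about pain while walking on 0 to 10, whereas the outcome is pain intensity on a scale ending at 9. If the two were mixed, with the screening score serving as baseline, a patient whose pain had not changed would appear to improve. One of the study's questions is how rehabilitation outcomes in knee osteoarthritis should be evaluated in future, so an instrument of uncertain range would also be hard to reuse.

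**Working it through.** **Inputs.** Stated count 9 and anchors 0 and 9 (Outcome Measures, item 1). Eligibility scale 0 to 10, called 11-point (Eligibility). WOMAC items 0 to 4 with five labels (Outcome Measures, item 2).

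**Counting response options** (maximum − minimum + 1):

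- Eligibility: 10 − 0 + 1 = 11, which matches the protocol.
- WOMAC item: 4 − 0 + 1 = 5, which matches the five labels.
- Primary pain scale: 9 − 0 + 1 = 10, which does not match nine.

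**Counting unit steps** (maximum − minimum):

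- Primary pain scale: 9 − 0 = 9, which matches.
- Eligibility: 10 − 0 = 10, which does not match 11.

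Nine can thus be recovered as a count of steps, but that is not how the protocol counts its eligibility scale. A scale with exactly nine scores would run 0 to 8 or 1 to 9. The first overrides the stated worst-pain anchor and the second the stated no-pain anchor.

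**Effect on the outcome.** Raw change is the week-6 score minus the baseline score. The number of points does not enter it. The count matters only if change is expressed as a share of the range and an anchor is also wrong:

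| Scale | One point | Two points |
|---|---|---|
| 0 to 9 (as anchored) | 1/9 = 11.1% | 2/9 = 22.2% |
| 0 to 8 or 1 to 9 | 1/8 = 12.5% | 2/8 = 25.0% |

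The ratio is 9/8 = 1.125.

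**Screening item.** By proportion, the entry cut of 3 on 0 to 10 corresponds to 3 × 9/10 = 2.7 on 0 to 9. No rule in the protocol makes that conversion. If a 0-to-10 screening score x were used as baseline, an unchanged patient would show a false fall of x − 0.9x = 0.1x, which is 0.4 points at x = 4 and 0.8 at x = 8. The outcome definition, however, puts the change from baseline on the VAS itself. On its natural reading both measurements come from that scale, and a screening score would not satisfy it.

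**The case for a change.** The strongest case for acting is that the protocol states the range of a primary outcome and states it inconsistently, which is not something normally left to an analysis plan. Reading nine as steps conflicts with the 11-point label in Eligibility. Reading it as a continuous line leaves the response format unclear. The document alone cannot prove which figure is wrong, and the remedy costs one look at the form and one word.

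Much of this stands. The mismatch is genuine, and the protocol's own usage counts against the step reading. That usage is thin, though: it rests on one label for a different instrument, since the WOMAC text lists five responses without using the word point. Loose wording is therefore unlikely but not excluded. The two possible errors are also not equally plausible. The anchors each carry a number and a meaning, while the count is a redundant descriptor and the likelier slip.

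The argument from the screening item does not stand. An entry criterion and an outcome may use different questions and scales, and the protocol draws no comparison between them. Using one scale throughout, or reporting change as a percentage of range, is a matter of preference or reporting detail.

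**Conclusion.** This is a clerical inconsistency that needs no change to the plan. The anchors 0 and 9 give ten scores where the text says nine. The most likely correct description is a ten-point scale from 0 to 9, which the form used would confirm. Correcting one word or digit would change neither what the trial did nor what it can conclude: patients' raw changes are unaffected, and nothing the protocol calculates or decides depends on the count.

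This rests on two assumptions: the same form was used at baseline and week 6, as the outcome definition implies, and the printed anchors are those on the form. If the second failed, each point would represent 12.5% of the range instead of 11.1%. That would be a matter of description in a single-group feasibility study of 17 patients, and an analyst with the form in hand would settle it when reporting.
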